## Study design

This is a retrospective cohort study using health insurance claims (outpatient and inpatient) data provided by Medical Data Vision Co., Ltd. (MDV) (Tokyo, Japan).

HRs for hospitalization due to CAP among incident users of Trelegy 100 compared to MITT is estimated by identifying and following patients without the pneumonia event at the index date (at risk).

In this study, data will be collected retrospectively with the 1,080-day identification period to have as much patient data as possible within the time frame to submit study results for the reexamination application for Trelegy 100. We plan to conduct data review in 2022 as described at the bottom of ABSTRACT, and we need time to agree on the protocol with PMDA after the endorsement by Protocol Review Committee (PRC), and thus we prepared this protocol in 2020.

## Population

Primary objective

Incident users of Trelegy 100 or MITT

Secondary objective-a) to c):

Overall users or incident users of Trelegy 100 or MITT.

Overall users refer to those have prescriptions of Trelegy 100 or MITT between May 22, 2019 (launch date of Trelegy 100) and May 5, 2022. The index date will be the first prescription date on or after May 22, 2019.

Incident users are subpopulation of overall users who do not have any triple therapies for 360 days before the index date.

Secondary objective-d):

COPD patients (regardless of treatment)

## Variables

### Exposures

There are two types of triple therapy: single inhaler triple therapy (SITT) (Trelegy 100 only) and MITT as described below. Exposures of this study are Trelegy 100 (SITT) and MITT.

1. Single inhaler triple therapy (SITT):
  - a. Trelegy 100 (Fluticasone furoate (FF)/Umeclidinium bromide (UMEC)/ Vilanterol trifrenatate (VI) delivered in an Ellipta inhaler)
  - b. SITTs other than Trelegy 100 (for secondary objective-d) only)
2. Multiple inhaler triple therapy (MITT):
  - a. LAMA combined with fixed dose ICS/LABA (two devices), or
  - b. Fixed dose LAMA/LABA with ICS (two devices), or
  - c. ICS, LABA, and LAMA (three devices)
  - d. Any other combinations of the 3 components (ICS, LAMA and LABA)

### Outcomes

Hospitalization due to CAP which occurs 1 day or more after the index date. Admission date will be treated as the first day of hospitalization due to CAP.

Hospitalization due to CAP during follow-up period (defined in 8.1 Study Design) will be identified using Diagnosis Procedure Combination (DPC) data. The International Statistical Classification of Diseases and Related Health Problems, Tenth Revision (ICD-10) codes, DPC

disease classification codes, prescription data and diagnostic imaging data will be used as follows.

#### Definition 1

- 1) Any of the ICD-10 codes of J10.0, J11.0 or J12-J18
- 2) The above ICD-10 codes in DPC disease segment #21 (disease which triggered the hospitalization)
- 3) Prescription of antibiotics (Anatomical Therapeutic Chemical (ATC) code: J01) on the day of admission or the next day of hospitalization
- 4) Diagnostic imaging (X-ray or computerized tomography (CT) scan) conducted between 2 days before and 7 days after the hospitalization

#### Definition 2 (for supplemental analysis only)

- 1) Any of the ICD-10 codes of J10.0, J11.0 or J12-J18
- 2) The above ICD-10 codes in DPC disease segment #21 (disease which triggered the hospitalization)
- 3) Prescription of antibiotic injection (ATC code): J01, dosage form code:4(injection) on the day of admission or the next day of hospitalization
- 4) Diagnostic imaging (X-ray or computerized tomography (CT) scan) conducted between 2 days before and 7 days after the hospitalization

If all of the above 1), 2), 3) and 4) are recorded on the same hospitalization, it is defined as “hospitalization due to CAP”. Medical/medical care-related pneumonia will be included if it meets the outcome definition. Although the JRS guideline recommends the use of injectable antibiotics, we considered that there might be a few patients who received oral antibiotics for the treatment of CAP. Therefore, in definition 1, we use oral antibiotics as well as injectable antibiotics to include those patients who were hospitalized due to CAP and received oral antibiotics. We also use definition 2 focusing on injectable antibiotics to include only patients who were treated according to the guideline.

### Data sources

Data will be derived from MDV database.

### Study size

From the sales forecast, the number of patients with the following treatment between May 22, 2019 and May 5, 2022 in MDV database is provided below:

- Trelegy 100 group: 6450 patients
- MITT group: 4370 patients

Considering inclusion and exclusion criteria (refer to “Sec 8.2.1 Inclusion criteria” and “Sec 8.2.2 Exclusion criteria”), the number of patients in this study is assumed to be from 30% to 50%.

- Trelegy 100 treatment: 1935 to 3225 patients
- MITT treatment: 1311 to 2185 patients

In primary analysis, HR for hospitalization due to CAP among incident Trelegy 100 users compared to incident MITT users within the 360-day follow-up period will be estimated along with 95% confidence intervals using Cox proportional hazard model (follow-up period will be up to 360 days in the base-case analysis). Probability of observing  $HR > 3$  is displayed for different scenarios in “Sec 8.5 Study Size”.

In secondary analysis, incidence rates for hospitalization due to CAP in Trelegy 100 and MITT groups within the 360-day follow-up period will be calculated along with 95% exact poisson confidence intervals using chi-square distribution (follow-up period will be up to 360 days in the base-case analysis). The expected 95% confidence intervals for incidence rate of hospitalization due to CAP for different scenarios are described in “Sec 8.5 Study Size”.

**Data analysis**

## Primary analysis

- ✓ HRs for hospitalization due to CAP among incident Trelegy 100 users compared to incident MITT users

## Secondary analysis

- ✓ Incidence rates of “hospitalization due to CAP” in Trelegy 100 or MITT groups
- ✓ Characteristics of patients in Trelegy 100 or MITT groups  
Age, gender, medical history/comorbidities, history of COPD treatments/exacerbation/pneumonia

For secondary objectives, both Trelegy 100 and MITT groups will be analysed in overall or incident users.

\*Overall users refer to those have prescriptions of Trelegy 100 or MITT between May 22, 2019 (launch date of Trelegy 100) and May 5, 2022. The index date will be the first prescription date on or after May 22, 2019.

Incident users are subpopulation of overall users who do not have any triple therapies for 360 days before the index date.

- ✓ Crude and adjusted HRs for “hospitalization due to CAP” by gender, age, calendar year of Index date, month of Index date, COPD treatments in look-back period, hospitalization due to COPD exacerbation in look-back period, hospitalization due to CAP in look-back period, comorbidities of pre-defined disease such as asthma, myocardial infarction, congestive heart failure, cerebrovascular disease, dementia, peptic ulcer, peripheral vascular disease, connective tissue disease, diabetes, anxiety, depression, BMI, smoking history, and execution of lung function test within Trelegy 100 or MITT group in overall or incident users.
- ✓ Proportion of triple therapy among COPD patients before the launch date of Trelegy 100 (May 22, 2019) and annually after the launch date (360 days prior to date of launch of Trelegy 100, and 0-359 days, 360-719 days, 720- 1079 days after the launch). Proportion of any ICS-containing therapies and comorbid asthma will be calculated as well. Target population for this objective includes COPD patients regardless of treatment.

**Milestones**

Milestone	Planned date
Start of data collection	May 22, 2019
End of data collection	Apr 30, 2023
Registration in the EU PAS register	To be determined (TBD)
Data extraction for data review	Sep 17, 2022
Data review	Dec 17, 2022
Data extraction for final report	Sep 17, 2023
Statistical analysis complete (End of Study)	Dec 17, 2023
Final report of study results	May 17, 2024

**4. AMENDMENTS AND UPDATES**

Amendment or update no	Date	Section of study protocol	Amendment or update	Reason
<1>	<Date>	<Text>	<Text>	<Text>
<2>	<Date>	<Text>	<Text>	<Text>
<n>	<Date>	<Text>	<Text>	<Text>

## 5. MILESTONES

Milestone	Planned date
Start of data collection	May 22, 2019
End of data collection	Apr 30, 2023
Registration in the EU PAS register	To be determined (TBD)
Data extraction for data review	Sep 17, 2022
Data review	Dec 17, 2022
Data extraction for final report	Sep 17, 2023
Statistical analysis complete (End of Study)	Dec 17, 2023
Final report of study results	May 17, 2024

## 6. RATIONAL AND BACKGROUND

### 6.1. Background

Trelegy 100 is a 3-component combination inhaler (Fluticasone furoate (FF)/Umeclidinium bromide(UMEC)/ Vilanterol trifenate(VI)) of FF, inhaled corticosteroid (ICS); UMEC, a long-acting muscarinic antagonist (LAMA); and VI, a long-acting beta2-agonist (LABA); for the treatment of Chronic obstructive pulmonary disease (COPD).

COPD is a progressive disease characterized by increased airflow obstruction caused by both peripheral airflow lesions and emphysematous lesions in complex manner with various degrees of contribution and causes progressive aggravation of respiratory symptoms such as dyspnea on exertion, chronic cough, and increased sputum. COPD is also known to significantly reduce patients' quality of life (QOL). Aggravation of COPD is generally considered to be an acute exacerbation of symptoms beyond the range of daily fluctuations that requires changes in treatment in a stable phase.

Aggravation of COPD reduces QOL and respiratory function of patients with COPD and worsens their vital prognosis.

COPD pharmacotherapy is helpful in improving symptoms and QOL, increasing (and maintaining) exercise tolerance and physical activity, and preventing exacerbations. The Global Strategy for the Diagnosis, Management, and Prevention of Chronic Obstructive Pulmonary Disease (2017 Revision), developed by Global Initiative for Chronic Obstructive Lung Disease (GOLD), recommended LAMA+LABA or LAMA+LABA+ICS as a preferred treatment for patients with severe symptoms of COPD and at-risk of exacerbation. The Japanese Respiratory Society (JRS) Guidelines for the Diagnosis and Treatment of COPD, 4th Edition (2013-Amendment) indicated that the mainstay of drug treatment was bronchodilators, and it was recommended that the use of ICS combination drugs be considered when exacerbations of COPD are repeated. Based on these findings, it was considered that ICS plus LAMA+LABA triple therapy should be used in patients with "recurrent exacerbations even with LAMA+LABA " or "patients with severe symptoms even when treated with ICS+LABA." Because the treatment of COPD is long-lasting and many patients get older and take more than one drug for other comorbidities, increasing adherence, such as adherence and treatment continuation rates, is critical for achieving good treatment outcomes. Trelegy 100, a 3-component inhalant, was also developed with the hope of improving patient convenience and contributing to improved adherence. The superiority of Trelegy 100 over UMEC/VI and FF/VI was verified in CTT116855(IMPACT) study, which is a phase 3 joint study, and there were no new safety concerns. Therefore, an application was submitted for marketing approval in Japan for the indication of remission of symptoms of COPD (chronic bronchitis/emphysema) (when concomitant use of ICS, inhaled LAMA, and inhaled LABA is required), and approval was obtained in March 2019.

The JRS Guidelines for the Diagnosis and Treatment of COPD, 5th Edition (2018 Revision) states that ICS-based drugs are used concomitantly with long-acting bronchodilators in asthma-complicated COPD. In general, the risk of developing pneumonia increases with treatments including ICS, so the use of this drug should be carefully determined according to the individual patient's condition.

Trelegy 100 is convenient because ICS, LAMA and LABA can be administered simultaneously with one inhalation, and the number of patients prescribed with "triple therapy" may increase compared to the past when only Multiple inhaler triple therapy (MITT) was available. It is important to investigate the risks of developing pneumonia when administering drugs in clinical practice and to ensure proper use. On consultation with the Pharmaceuticals and Medical Devices Agency (PMDA), we decided to conduct a database-study for CAP requiring hospitalization.

### 6.2. Rationale

This study must be conducted as an approval condition under Japan regulation.

## 7. RESEARCH QUESTION AND OBJECTIVE(S)

### Primary objectives

Compare the occurrence of hospitalization due to community-acquired pneumonia (CAP) among patients with COPD who were incident users of Trelegy 100 or MITT. Hazard ratio (HR) will be calculated to investigate if the risk of CAP in Trelegy 100 group is not higher than a certain level (HR>3) compared to MITT group.

### Secondary objectives

- a) Estimate the incidence rate of hospitalization due to CAP among COPD patients who were treated with Trelegy 100 or MITT. Overall, or incident triple use patients will be analysed in Trelegy 100 group and MITT group, respectively.
- b) Describe characteristics of COPD patients who were treated with Trelegy 100 or MITT. Overall, or incident triple use patients will be analysed in Trelegy 100 group and MITT group, respectively.
- c) Calculate crude and adjusted HRs for hospitalization due to CAP within Trelegy 100 or MITT group for each covariate, with one of the covariate subgroups serving as the reference group. Each model would be adjusted for all the other stated covariates. Overall, or incident triple use patients will be analysed in Trelegy 100 group and MITT group, respectively.  
In the model, following subgroups will be considered;  
gender, age, calendar year of Index date, month of Index date, COPD treatments in look-back period, hospitalization due to COPD exacerbation in look-back period, hospitalization due to CAP in look-back period, comorbidities of pre-defined disease such as asthma, myocardial infarction, congestive heart failure, cerebrovascular disease, dementia, peptic ulcer, peripheral vascular disease, connective tissue disease, diabetes, anxiety, depression, body mass index (BMI), smoking history, and execution of lung function test within Trelegy 100 or MITT group.
- d) Describe change over time in the expansion of triple therapy, use of an ICS-containing medications, and proportion of asthma comorbidity among COPD patients. Over-time refers to 360 days prior to date of launch of Trelegy 100, and 0-359 days, 360-719 days, 720- 1079 days after the launch. Target population for this objective includes COPD patients regardless of treatment.  
\*Overall users refer to those have prescriptions of Trelegy 100 or MITT between May 22, 2019 (launch date of Trelegy 100) and May 5, 2022. The index date will be the first prescription date on or after May 22, 2019.

Incident users are subpopulation of overall users who do not have any triple therapies for 360 days before the index date.

Trelegy 100 is convenient because ICS, LAMA and LABA can be administered simultaneously with one inhalation, and the number of patients prescribed with “triple therapy” may increase compared to the past when only MITT was available. By considering this situation, it makes sense to examine risks for pneumonia in patients treated with Trelegy 100 in real world.

Based on the definition of the follow-up period described in “Sec 8.1 Study Design”, there will be large variation in the observational period among patients. Thus the incidence rate is appropriate for measuring occurrence of pneumonia, and HR is appropriate for comparing the pneumonia occurrence between Trelegy 100 or MITT group.

## 8. RESEARCH METHODS

Patients will be identified between May 22, 2019 and May 5, 2022 (1080 days).

[figure not shown]
For patient identification, visit records are required in two periods; (1) within 360 days (look-back period) prior to the date of onset of treatment (index date), and (2) within 180 days prior to the look-back period. Follow-up period will be maximum 360 days after the index date, therefore the end of study period will be Apr 30, 2023. Sensitivity analysis will be performed on patients who will have a 1,440-day follow up.

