**Figure1 Study design**

Identification of the study population will be conducted using health insurance claims data (outpatient and inpatient) and Diagnosis Procedure Combination (DPC) data. Patients surveyed are aged 40 years or older at the start date of prescription (index date) for Trelegy 100 or MITT during the 1,080-day identification period (from May 22, 2019 to May 5, 2022).

In this protocol, one month is defined as 30 days based on the manner of Post-marketing Surveillance in Japan.

In this study, data will be collected retrospectively with the 1,080-day identification period to have as much patient data as possible within the time frame to submit study results for the reexamination application for Trelegy 100. We plan to conduct data review in 2022 as described at the bottom of ABSTRACT, and we need time to agree on the protocol with PMDA after the endorsement by Protocol Review Committee (PRC), and thus we prepared this protocol in 2020.

Patients with records of International Statistical Classification of Diseases and Related Health Problems, Tenth Revision (ICD -10) codes for COPD (J42, J43 or J44), one record at the index date and additional 2 records (outpatient visit or hospital admission) in the 360 days look-back period [index date, index date -360 days]. This criterion is to exclude patients with infrequent visits and to secure collection of patient characteristics data in the look-back period.

At least one record (outpatient visit or hospital admission) with any ICD-10 codes in the 180 days

prior to the start date of look-back period [index date – 360 days, index date – 540 days]. This criterion is to secure patient records throughout the look-back period.

Follow-up period will be from the index date (including the index date) to the earliest date of the followings: 1) admission date of hospitalization due to CAP or 2) date of death or 3) end date of exposure period with Trelegy 100 or MITT by discontinuation (defined in 8.3.1.1. continuation of exposure), or 4) 360 days after the index date.

In base case analysis, the 360-day follow-up period will be applied, while the 1,440-day follow-up period will be used in sensitivity analysis.

The reason for the 360-day follow-up period is based on the article by Suissa et al. which demonstrated that the effect of ICS on pneumonia occurrence among COPD patients peaked in the first year of use.

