### 8.3.1.1. Continuation of exposure

[figure not shown]

Figure3 Exposure period

- 1) Gap (variable): Actual period between 2 consecutive prescriptions
- 2) Grace period (constant): The threshold used to determine if an interruption in therapy causes a patient to be considered non-persistent

Continuation of exposure will be defined by using “prescription period”, “gap” and “grace period” (see Figure3).

Prescription period: Treatment period estimated by dosage in package insert (as described in a separate “statistical analysis plan”)

Gap: Actual period between 2 consecutive prescription periods

Grace period: The threshold used to determine discontinuation of treatment

In this study, we set the “grace period” at 30 days.

If a gap between 2 consecutive prescription periods is 30 days or less, the treatment is considered continuation.

If a gap between 2 consecutive prescription periods is 31 days or more, the treatment is considered discontinuation.

Japan’s medical fee system recommends careful consideration for long-term prescription more than 30 days. Restrictions on prescription period for 14 days right after the launch was not applied to Trelegy 100. Based on these situations, we regarded 30 days as a standard prescription period for both Trelegy 100 and MITT. By considering 30-day prescription, potential delay in physician visits and missing medicine, the grace period was set to 30 days.

Exposure period in follow-up period will be defined as the period starting at the index date and ending at 30 days (grace period) after the end date of the final prescription period\* of Trelegy 100 or MITT during 360 days after the index date. If the final prescription period starts before the end date of the previous prescription period, the overlapped days of the 2 prescription periods will be added to the grace period (30 days) in calculating the end date of the final prescription period.

\*Final prescription period of Trelegy 100 or MITT will be defined as follows:

- 1) Subsequent prescription period of Trelegy 100 or MITT started 31 days or more (longer than grace period) after the end date of the last prescription period. In MITT group, the end date of the last prescription period is the end date of overlapping prescription period.
- 2) MITT includes a variety of combination of ICS/LAMA/LABA, and only the change in components of MITT is not considered discontinuation.

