## 8.4. Data Sources

The proposed study will be conducted using the Japanese MDV hospital claims database. MDV is a Japanese company specializing in integrated medical systems that manages a large administrative database constructed from hospitals (mainly tertiary) in Japan. The MDV data cover around 25% of acute care hospitals in Japan (439 hospitals) and include both inpatient and outpatient services. For the cumulative period between April 2008 and February 2021, the database has over 35.7 million patients, making it one of the largest Japanese healthcare datasets.

This study will use all available data between November 2017 and Apr 2023 in the MDV hospital claims database to assess the proposed study objectives. The data is updated monthly, thereby minimizing the time lag for data access and analyses. The database contains disease diagnoses, claims for medical procedures and pharmacy prescriptions (from inpatient and outpatient services in the hospitals covered), and laboratory test results available for approximately 10% of patients. As this study will only use de-identified data, approval from an institutional review board (IRB) will not be necessary for the conduct of this study.

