#### **8.7.3.3. Sensitivity analysis**

The primary endpoints and explanatory analysis will be performed by the following conditions. When one of the 3 conditions are applied, other 2 conditions will not be applied but original conditions will be kept.

- One of inclusion criteria is changed from “patients with ICD-10 codes for COPD (J42, J43 or J44)” to “patients with ICD-10 codes for COPD (J42, J43 or J44) and with prescription of any inhaled medicine with the indication of COPD”, at the index date and on at least 2 visits (outpatient visit or hospital admission) in the look-back period
- Overlap of 3 components for MITT group is changed from at least 1 day to at least 14 days (including the index date)
- Follow-up period is changed from maximum 360 days to maximum 1,440 days (after the index date)

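### Section 8 and section 8.7.3.3 define the 1,440-day sensitivity analysis differently, and the follow-up rule does not stop at the end of data

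*Protocol*

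**What the plan says.** Three places in the protocol describe the long-follow-up sensitivity analysis.

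- Section 8 (opening): "Sensitivity analysis will be performed on patients who will have a 1,440-day follow up".
- Section 8.1, below Figure 1: "In base case analysis, the 360-day follow-up period will be applied, while the 1,440-day follow-up period will be used in sensitivity analysis".
- Section 8.7.3.3: "Follow-up period is changed from maximum 360 days to maximum 1,440 days (after the index date". The same section says that when one of its three conditions is varied, everything else stays as in the base case.

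The calendar is fixed in section 8: "Patients will be identified between May 22, 2019 and May 5, 2022 (1080 days" and "Follow-up period will be maximum 360 days after the index date, therefore the end of study period will be Apr 30, 2023". Section 8.4 agrees: "This study will use all available data between November 2017 and Apr 2023 in the MDV hospital claims database".

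Under section 8.1, follow-up runs from the index date, inclusive, to the earliest of four stops: a CAP admission, death, the end of exposure through discontinuation, or day 360. The end of data is not among them. Section 8.3.1.1 has exposure "ending at 30 days (grace period) after the end date of the final prescription period" and takes 30 days as the standard prescription length for both groups.

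**The concern.** Two separate things look wrong.

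First, the population. Section 8 selects patients by how much follow-up they will have, while section 8.7.3.3 changes only the cap for all patients. Section 8.1 does not settle which is meant. The section 8 version leaves almost nobody. It also conditions on the future: under the section 8.1 stops, a patient who accrues 1,440 days has had no CAP admission, no death and no discontinuation before then, so such a group is close to event-free by construction.

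Second, the censoring. The stop list is written as complete. In the base case the 360-day cap keeps every patient inside the data. Once the cap becomes 1,440 days and nothing else changes, that protection is lost. Patients still on treatment when the data end stay in the risk sets for a stretch in which no CAP admission could be seen.

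At stake is one of the three prespecified sensitivity analyses of the primary endpoint, and the only one that looks past the first year.

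**Working it through.** **Inputs.** Index dates May 22, 2019 to May 5, 2022, and data end Apr 30, 2023 (section 8); caps of 360 and 1,440 days (sections 8.1 and 8.7.3.3); standard supply of 30 days and grace of 30 days (section 8.3.1.1).

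**1. The plan's own figures.** May 22, 2019 to May 5, 2022, both dates counted, is 1,080 days. May 5, 2022 + 360 days = Apr 30, 2023. Both match the protocol. Also 1,080 + 360 = 1,440, so 1,440 days is the longest window that the calendar allows.

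**2. Who can have 1,440 days.** May 22, 2019 to Apr 30, 2023 is 1,439 days after index, or 1,440 counting both ends.
- Index date counted as day 1: 1 of 1,080 index dates qualifies (0.09%).
- Index date + 1,440 days (May 1, 2023): 0 of 1,080 qualify.

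If starts were uniform (an assumption), the larger projected incident cohorts in section 8.5 would give 3,225/1,080 ≈ 3.0 Trelegy 100 starters and 2,185/1,080 ≈ 2.0 MITT starters on launch day, before any CAP, death or discontinuation.

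**3. The analysis as section 8.7.3.3 words it.** Days available to the data end run from 360 (last index date) to 1,439 (launch day), with a mean of 899.5 over the 1,080 dates. Every index date contributes.

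**4. Where the cap falls.** With 360 days, it never passes Apr 30, 2023. With 1,440 days, it passes the data end for 1,079 of 1,080 index dates (index date as day 1) or for all 1,080.

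**5. Overrun per patient.** For a patient still treated at the cut, the remaining stop is the end of exposure, so overrun = remaining supply + 30 days.
- A 30-day prescription issued on Apr 30, 2023 leaves 29 days of supply after that date, and 29 + 30 = 59 days (60 if supply is counted from the next day).
- The average for a patient in mid-supply is about 15 + 30 = 45 days. Someone already in the grace period overruns by less than 30.
- With assumed supplies of 60 or 90 days, the maximum is 89 or 119 days.

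Section 8.3.1.1 adds overlapping days from early refills to the grace period. That would lengthen these figures and is not included here.

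**6. Share of counted person-time.** Simulation with uniform starts, constant discontinuation, and no CAP or death. Supply lengths other than 30 days and all persistence values are assumptions.

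| Supply | 1-year persistence 30% | 50% | 80% |
|---|---|---|---|
| 30 days | 1.2% | 2.2% | 3.6% |
| 60 days | 1.6% | 2.9% | 4.8% |
| 90 days | 2.1% | 3.6% | 5.9% |

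**7. Cross-check.** If a share p is still treated at the cut, the added time is 45p. If one non-increasing persistence curve applies to all start dates, mean follow-up is at least 899.5p. The inflation therefore cannot exceed 45/899.5 = 5.0% with 30-day supplies. With constant discontinuation, p = 20% implies mean follow-up of about 401 days and 9/401 = 2.2%; p = 40% implies about 555 days and 18/555 = 3.2%.

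**8. What this could do to a comparison.** Only a difference between the groups matters. Take the widest contrast in the 30-day row and look at the crude rate ratio, Trelegy 100 over MITT. With 80% persistence on Trelegy 100 and 30% on MITT, the ratio is multiplied by (1 − 0.0364)/(1 − 0.0124) = 0.976. With the groups swapped, the factor is 1.025. This illustrates size and sign for crude rates; it is not a calculation of the Cox HR.

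**The case against.** Section 8.7.3.3 is where the sensitivity analyses are specified, and it plainly says maximum. The sentence in section 8 is an overview beside a figure that is not reproduced in the text at hand. Since 1,440 is exactly the launch-to-data-end window, the authors very probably meant an upper limit set by the data. The data end is stated in sections 5, 8 and 8.4, the glossary defines an observational period as time observable in the data source, and data handling is deferred to the SAP, which was not available here and may name the stop. The base case is untouched.

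Most of this stands. It shows the likely intent, and it rules out three stronger readings that a reader might infer.

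- *The analysis must be empty.* This follows only from the section 8 sentence. Under section 8.7.3.3 every index date contributes 360 to 1,439 days.
- *All of the 1,440-day window beyond the data is counted.* With uniform starts, about 37.5% of the nominal window lies after Apr 30, 2023. The exposure rule limits what is counted to remaining supply plus grace.
- *The HR is biased in favour of Trelegy 100.* That needs better persistence or later starts in that group. The documents give no persistence or start-date figures by group, and step 8 shows that the sign reverses with the assumption. Nor can 40% still treated be paired with a 300-day mean follow-up to reach 18/300 = 6%, since 40% still treated implies at least 0.40 × 899.5 = 360 days.

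What does not stand is that nothing needs changing. Deferring detail to the SAP does not reconcile two conflicting sentences in the protocol. The stop list in section 8.1 is set out in full, and section 8.7.3.3 carries it over with only the cap altered. Neither the study end date nor the glossary term is invoked in that rule.

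**Conclusion.** The point holds as a conflict of wording plus an incomplete censoring rule, both confined to the 1,440-day sensitivity analysis. Read literally, section 8 fits at most 1 of 1,080 index dates and selects on future event-free persistence. Section 8.7.3.3 gives a workable analysis, but the section 8.1 stops applied to it count up to about 60 unobservable days for each patient still treated at the cut, with 30-day supplies.

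The resulting inflation of person-time is a few percent: 1.2% to 3.6% with the protocol's standard supply, and up to 5.9% with 90-day supplies and 80% persistence. These figures rest on assumed persistence, supply lengths and uniform starts. The effect on the HR depends on differences between the groups that the documents do not give.

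The primary 360-day HR is unaffected. Severity is minor.

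**What to change.** Two sentences.

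1. In section 8, replace the sentence on the sensitivity analysis so that it matches section 8.7.3.3: all base-case patients are included, and each is followed for up to a maximum of 1,440 days after the index date.
2. In section 8.1, add a fifth stop to the follow-up rule: the end of the study period, Apr 30, 2023. It changes nothing in the base case and closes the gap in the 1,440-day analysis.

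Neither change needs further data or alters the primary analysis. If the SAP already censors at the end of data, the second edit only brings the protocol into line with it.
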